#### **9.5 Post-operative treatment:**

Post-operative treatment is at the discretion of the treating physicians. Participation in subsequent adjuvant clinical trials is allowed.

#### **9.6 Biomarker Assessment:**

Baseline formalin fixed paraffin embedded (FFPE) tissue block will be obtained from the diagnostic breast biopsy to collect 4 unstained slides and an additional single tissue core (ranging from 0.6mm to 4.0mm in diameter, obtained with a microarray instrument). In addition, a tissue block from the residual tumor tissue will be obtained from the surgical specimen to collect 10 unstained slides and an additional single tissue core (ranging from 0.6mm to 4.0mm in diameter, obtained with a microarray instrument).

Specimens collected at Yale University Cancer Center will be shipped to the following address:

ATTN: [name]  
[name]  
[name]

Specimens collected at Thomas Jefferson University Sidney Kimmel Cancer Center will be shipped to the following address:

ATTN: [name]  
Main Building  
[name]  
[name]

All samples collected as part of this study will be sent to the address above at Thomas Jefferson University for storage at the end of the study. The samples from the baseline biopsies and the surgical specimens will be used (when feasible) for measurement of Ki67 and research analyses. Ki67 analysis will be performed at any Clinical Laboratory Improvement Amendments (CLIA) certified laboratory including the Yale Specialized Translational Services (STS) laboratory. ER expression will be repeated on the surgical specimen for PEPI score calculation. The planned molecular analysis of these tissues may include gene expression profiling, and PI3K pathway biomarkers by Automated Quantitative Analysis to develop an assay that may predict response or resistance to an everolimus and aromatase inhibitor combination. Candidate markers include pS6, mTOR, p4E-BP1, pAKT and APC.

### **9.7 End of Study Evaluation**

Once post-operative therapy is completed, the final study follow up visit will be within 4-6 weeks after completion of surgery and will include:

- Complete review of systems and medical history including ECOG performance status assessment, endocrine therapy related AE assessment and record concomitant medications
- Physical examination including measurement of weight and vital signs including oxygen saturation by pulse oximetry.
- CBC, including differential and platelets, serum albumin, calcium, phosphorus, BUN, creatinine, total bilirubin, alkaline phosphatase, LDH, AST, ALT, Na, K, Cl, CO2 assessment and fasting glucose.
- Complete microscopic urine analysis
- PTT, PT and INR

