### **11.2 Safety Assessment and Follow-Up**

The PI will follow adverse events with start dates occurring any time after informed consent is obtained until 7 (for non-serious AEs) or 30 days (for SAEs) after the last day of study participation. At each study visit, the investigator (or designee) will inquire about the occurrence of AE/SAEs since the last visit. Events will be followed for outcome information until resolution or stabilization.

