### **11.3 Recording Adverse Events**

The following subsections detail what information must be documented for each adverse event occurring during the time period specified in Section 11.4.

At each contact with the subject, the investigator must seek information on adverse events by specific questioning and, as appropriate, by examination. Information on all adverse events should be recorded immediately in the source document, and also in the appropriate adverse event module of the case report form (CRF). All clearly related signs, symptoms, and abnormal diagnostic procedures results should be recorded in the source document, though should be grouped under one diagnosis.

All adverse events occurring during the study period must be recorded.

The clinical course of each event should be followed until resolution, stabilization, or until it has been determined that the study treatment or participation is not the cause. Serious adverse events that are still ongoing at the end of the study period must be followed up to determine the final outcome. Any serious adverse event that occurs after the study period and is considered to be possibly related to the study treatment or study participation should be recorded and reported immediately.

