## 11.4 Safety Reporting

The study period during which adverse events must be reported is normally defined as the period from the initiation of any study procedures to the end of the study treatment follow-up. For this study, the study treatment follow-up is defined as 30 days following the last administration of study treatment.

For patients whose Oncotype Dx recurrence score is unknown and who sign the molecular pre-screening ICF, AEs which occur after signature of this consent will only be captured if they meet the definition of serious as outlined in Section 11.1.2 and are reported to be causally related with study procedures (e.g. an invasive procedure such as biopsy). Once the main study ICF is signed, all AEs per the descriptions below will be captured in the Adverse Event CRF.

Patients whose Oncotype Dx recurrence score is known will sign the main study ICF.

For patients with unknown Oncotype Dx Recurrence Scores and who sign the molecular pre-screening ICF, SAE collection will start upon signing the molecular pre-screening ICF. SAEs will only be reported if the event is suspected to be causally related to a study procedure as assessed by the investigator (e.g. an invasive procedure such as biopsy). SAEs will be followed until resolution or until clinically relevant improvement or stabilization. If the main ICF is not signed (molecular screen failure), SAE collection ends 30 days after the last study related procedure.

For patients with known Oncotype Dx Recurrence Scores who sign the main study ICF, SAE collection starts at time of main study informed consent whether the patient is a screen failure or not.

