### **14.2 Secondary Endpoint**

1. Clinical and radiographic response rate will be assessed by two measures. Radiographic tumor size measurements by MRI (or ultrasound when MRI not feasible) and physical examination after completion of all chemotherapy compared to baseline. Response will be categorized following RECIST criteria (Appendix A). The results will be reported as descriptive statistics with 95% confidence intervals.

2. Toxicity will be recorded using the standard NCI Common Toxicity Criteria as per <http://ctep.cancer.gov/forms/CTCAEv4.pdf>. Results will be reported in a tabular format by worst grade and occurrence per patient over the entire study period
3. Measurements of Ki67 at baseline and after completion of neoadjuvant therapy.
4. Baseline and residual cancer tissue will be collected for future biomarker analysis. Considering the small sample size of the study the biomarker results will be exploratory and hypothesis generating. The planned molecular analysis of these tissues may include gene expression profiling, and PI3K pathway markers.

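### Section 9.7 gives the final visit two anchors that can conflict, and Sections 11.2 and 11.4 end the adverse event period differently, so the window of the worst-grade toxicity table in 14.2 is inconsistently defined

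*Combined protocol and SAP*

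**What the plan says.** **Final visit.** Section 9.7: "Once post-operative therapy is completed, the final study follow up visit will be within 4-6 weeks after completion of surgery". The visit includes an assessment of AEs related to endocrine therapy, laboratory tests and urinalysis.

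**What follows surgery.** Section 9.5: "Post-operative treatment is at the discretion of the treating physicians", and "Participation in subsequent adjuvant clinical trials is allowed". No duration is given. The Section 10 calendar marks post-operative treatment in the End of Study Evaluation column and does not choose an anchor for the visit.

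**AE period.** Section 11.4: "The study period during which adverse events must be reported is normally defined as the period from the initiation of any study procedures", running to the end of study treatment follow-up; then, "For this study, the study treatment follow-up is defined as 30 days following the last administration of study treatment". Section 11.3 relies on that rule for what "must be documented for each adverse event occurring during the time period specified in Section 11.4". Section 11.2, however, has AEs followed "until 7 (for non-serious AEs) or 30 days (for SAEs) after the last day of study participation". The documents do not define that last day.

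**Analysis.** Section 14.2, item 2, on toxicity: "Results will be reported in a tabular format by worst grade and occurrence per patient over the entire study period". It does not refer to 11.2, 11.4 or 9.7.

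**The concern.** The 9.7 sentence ties one visit to two events. If post-operative therapy is still running six weeks after surgery, a site can satisfy one condition but not both. With two centres, one might wait for therapy to finish while the other goes by the date of surgery. Final AE review and laboratory tests would then be taken at different times, some of them after treatment that is not part of the protocol.

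This reaches the analysis through Section 14.2. Tolerability is the first secondary objective, and its main summary is a worst-grade table. A worst-grade summary can only rise as the window lengthens, and in a single-arm trial there is no comparator against which added toxicity could be recognised. If the window follows participation rather than study treatment, two kinds of non-protocol toxicity can enter the table: from post-operative therapy, and from chemotherapy given after progression. Sections 9.3 and 9.4 allow such chemotherapy, and the calendar footnote still has patients who stop for progression followed through surgery and the end of study visit.

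**Working it through.** The plan gives no figure to reproduce here. The check is calendar arithmetic in days after the last dose of study treatment.

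**Inputs**
- Surgery: 3 to 8 weeks after the last dose of aromatase inhibitor and everolimus (Section 10, footnote 15). Section 9.4 gives the same 3 to 8 weeks but counts from the last chemotherapy; the footnote is used because it names the study drugs.
- Final visit on the surgery anchor: 4 to 6 weeks after surgery (9.7).
- AE period under 11.4: closes on day 30.
- AE follow-up under 11.2: 7 days (non-serious) or 30 days (serious) after the last day of participation. Assumption: that day is the final visit.

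**Step 1. Surgery.** 3 × 7 = day 21 to 8 × 7 = day 56.

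**Step 2. Final visit, surgery anchor.** (3 + 4) × 7 = day 49 to (8 + 6) × 7 = day 98.

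**Step 3. Against 11.4.** 49 − 30 = 19 and 98 − 30 = 68. The visit at which AEs are assessed falls 19 to 68 days after the 11.4 period has closed. Day 30 lies between 9 days after surgery (30 − 21) and 26 days before it (56 − 30).

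**Step 4. Against 11.2.** Non-serious events: 49 + 7 = day 56 to 98 + 7 = day 105. Serious events: 49 + 30 = day 79 to 98 + 30 = day 128.

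| Rule | End of AE window, days after last dose |
|---|---|
| 11.4 | 30 |
| 11.2, non-serious, surgery anchor | 56 to 105 |
| 11.2, serious, surgery anchor | 79 to 128 |
| 11.2, visit waits for post-operative therapy | no upper limit |

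**Step 5. The other anchor.** If post-operative therapy ends L weeks after surgery, a visit that waits for it falls no earlier than week L. For L above 6 the two conditions in 9.7 exclude each other. The documents give no L. Purely as an illustration, L = 12 to 24 would delay the visit by at least 12 − 6 = 6 and up to 24 − 4 = 20 weeks relative to the surgery anchor. The 11.2 end would move with it; the 11.4 end would stay at day 30.

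**Step 6. Weight of one patient.** 1/27 = 3.7 points if the table covers the 27 eligible patients; 1/33 = 3.0 points if it covers all 33 who may be enrolled. Section 14.2 does not state the denominator.

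**The case against.** A reader might infer from 9.7 that the end of the toxicity window is undefined. The documents do not support that. Section 11.4 defines a study period for AEs and closes it 30 days after the last study treatment, 11.3 points to it, and 14.2 uses the term study period. On that reading the 9.7 visit cannot move the cut-off, and post-operative toxicity could enter for at most the 9 days in Step 3. This part of the objection stands: the period is defined, though not consistently.

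A reader might also infer that months of adjuvant toxicity will be pooled into the table. That happens only if 11.4 is set aside in favour of participation. The 9.7 visit asks for AEs related to endocrine therapy rather than all AEs, and 11.3.1 requires relatedness to be judged for every event with concomitant therapy in mind. These points reduce the risk. They do not remove it, because 14.2 does not restrict the table to related events.

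Finally, the opening clause of 9.7 may be a drafting slip: the only numeric window is 4 to 6 weeks after surgery, and the calendar places the visit directly after surgery. That is plausible, but no passage says so.

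What the objection does not answer is that 11.2 states a different end from 11.4, and that 11.4.3 adds a further wording for serious events, counting from the stop of treatment or participation. Section 8 mentions a 30-day safety visit that has neither an entry in Section 9 nor a column in the calendar. The protocol also schedules an AE assessment after its own 11.4 period has ended.

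**Conclusion.** The point holds as an internal inconsistency. The two conditions in 9.7 cannot both be met when post-operative therapy runs beyond six weeks after surgery. The AE period ends on day 30 under 11.4 but, if participation ends at the final visit, on days 56 to 128 under 11.2 with the surgery anchor, and without limit under the other anchor. Section 14.2 does not say which applies.

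The effect on the toxicity table cannot be computed: the documents give neither the length of post-operative therapy nor the number of patients who will receive non-protocol treatment while still being followed. The 3.0 to 3.7 points is the weight of one patient, not an estimate of bias. The day counts rest on the 3 to 8 and 4 to 6 week windows being kept; the 11.2 range also rests on the stated assumption about participation.

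The primary PEPI-0 analysis and the two-stage design are untouched. The matter should be settled before toxicity is tabulated, because the choice of window could otherwise be made with the data in view.

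**What to change.** - Reconcile Section 9.7 and the Section 10 calendar so that the final visit has a single anchor. Which anchor is for the sponsor and investigators to decide.
- Reconcile 11.2 with 11.4, and define the last day of participation if the term is kept.
- In 14.2, item 2, replace the reference to the whole study period with one named AE cut-off consistent with 11.4.
- List separately any event after that cut-off or after the start of non-protocol anticancer therapy, whether given after surgery or after progression. The second condition is needed because chemotherapy for progression could begin within 30 days of the last study dose, inside the 11.4 window.

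The cost is a few sentences and one extra listing. Sample size and the primary analysis do not change.

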## 10 STUDY CALENDAR

	Baseline	W1	W5	W9	W13	W17	W21	W25	W26	Surgery	End of Study Evaluation
Pathology											
FFPE Tissue 	X									X	
Imaging											
Bilateral Mammogram 	X										
MRI of Involved Breast 	X				X 				X 		
12-lead ECG	X										
CT scan chest/abd 	X										
Bone scan 	X										
Bone Density Assessment 	X										
Treatment											
Aromatase Inhibitors 		X	X	X	X	X	X	X	X		
Everolimus		X	X	X	X	X	X	X	X		
Surgery 										X	
Post-operative treatment 											X

*\*Study subjects who come off treatment for progression or toxicity, should be followed through surgery and end of study visit. For study subjects who come off treatment for toxicity, continue to follow for up to 4 weeks or until resolution of toxicity.*

1. ER/PR/HER2 receptor from diagnostic biopsy results will be collected. Receptor status can be performed at any time prior to starting study treatment.
2. Oncotype Dx recurrence score from diagnostic biopsy will be collected. Oncotype Dx analysis can be performed at any time prior to starting study treatment.
3. Complete history and review of systems and documentation of the date of the last dose of endocrine or chemotherapy received before entering the study (baseline).
4. Complete physical examination including measurements of height (only at baseline), weight, and vital signs including oxygen saturation by pulse oximetry.

5. Record breast tumor and axillary node measurements by physical exam for palpable tumors. If suspicious lymph nodes are detected clinically or by imaging, a diagnostic image guided fine needle aspiration or biopsy of the suspicious node is required.
6. Study drug compliance assessment including dose and any treatment interruption.
7. For high risks subjects only. See exclusion criteria # 10.
8. Baseline fresh frozen formalin fixed paraffin embedded (FFPE) tissue block will be obtained from the diagnostic breast biopsy to collect 4 unstained slides and an additional single tissue core (ranging from 0.6mm to 4.0mm in diameter, obtained with a microarray instrument). In addition, a tissue block from the residual tumor tissue will be obtained from the surgical specimen to collect 10 unstained slides and an additional single tissue core (ranging from 0.6mm to 4.0mm in diameter, obtained with a microarray instrument).
9. Mammogram should be done within 4 weeks prior to start of treatment. Mammogram is to be done with clip placement to mark tumor bed. Breast imaging may be repeated any time during therapy if clinical suspicion of progression of disease.
10. Or a unilateral ultrasound of the involved breast if a patient is unable to have a breast MRI due to claustrophobia, metal in body, or lack of insurance coverage, etc. Breast imaging may be repeated any time during therapy if clinical suspicion of progression of disease.
11. The involved breast, and axilla (in patients with enlarged axillary nodes at baseline), will be reimaged by MRI between weeks 12 and 13 and again after completing neoadjuvant therapy. If a patient is unable to have a breast MRI, a breast ultrasound will be used to replace MRI at baseline, at 12-13 weeks and after completing neoadjuvant therapy. Other imaging, such as ultrasonography or MRI, is at the discretion of the treating physicians.
12. For clinical stage III or symptomatic stages II
13. Bone density assessment (within 12 months). If results of baseline bone density confirm evidence of osteoporosis, treatment for osteoporosis will be left to the discretion of the treating physician.
14. Standard dose of one of the following aromatase inhibitors (physician's choice): Anastrozole 1 mg, Letrozole 2.5 mg, Exemestane 25 mg.
15. Surgery will be scheduled 3-8 weeks after completion of last dose of aromatase inhibitor and everolimus. Patients with evidence of tumor response (including stable disease): Patients completing 26 weeks of neoadjuvant AI plus everolimus who are deemed resectable will undergo surgery. The decision regarding lumpectomy or mastectomy will be at the discretion of the treating surgeon. All patients will have axillary lymph node sampling with a technique that is deemed appropriate by the treating surgeon (refer to protocol).
16. B) Patients with evidence of disease progression during therapy: Patients who progress clinically or by imaging assessment during therapy will be removed from protocol treatment and further treatment including immediate referral to surgery or additional

chemotherapy will be at the discretion of the treating physician. Response to any subsequent preoperative therapy and findings at surgery will be recorded (refer to protocol).

17. Post-operative treatment is at the discretion of the treating physicians. Participation in subsequent adjuvant clinical trials is allowed.

## 11 Evaluation of Safety

Information about all adverse events, whether volunteered by the subject, discovered by investigator questioning, or detected through physical examination, laboratory test or other means, will be collected and recorded and followed as appropriate.

### 11.1 Specification of Safety Parameters

#### 11.1.1 Unanticipated Problems

Unanticipated problems (UAPs) include, in general, any incident, experience, or outcome that meets the following criteria:

- unexpected in terms of nature, severity, or frequency given (a) the research procedures that are described in the protocol-related documents, such as the IRB-approved research protocol and informed consent document; and (b) the characteristics of the participant population being studied;

UAPs are considered to pose risk to participants or others when they suggest that the research places participants or others at a greater risk of harm (including physical, psychological, economic, or social harm) than was previously known or recognized.

#### 11.1.2 Adverse Event

An adverse event is any untoward or unfavorable medical occurrence in a human participant, including any abnormal sign (for example, abnormal physical exam or laboratory finding), symptom, or disease, temporally associated with the participant's participation in the research, whether or not considered related to the participant's participation in the research.

#### 11.1.3 Laboratory test abnormalities

Laboratory abnormalities that constitute an Adverse event in their own right (are considered clinically significant, induce clinical signs or symptoms, require concomitant therapy or require changes in study treatment), should be recorded on the Adverse Events CRF. Whenever possible, a diagnosis, rather than a symptom should be provided (e.g. anemia instead of low hemoglobin). Laboratory abnormalities that meet the criteria for Adverse Events should be followed until they have returned to normal or an adequate explanation of the abnormality is found. When an abnormal laboratory or test result corresponds to a sign/symptom of an already reported adverse event, it is not necessary to separately record the lab/test result as an additional event.

Laboratory abnormalities, that do not meet the definition of an adverse event, should not be reported as adverse events. A Grade 3 or 4 event (severe) as per CTCAE does not automatically indicate a SAE unless it meets the definition of serious as defined below and/or

as per investigator's discretion. A dose hold or medication for the lab abnormality may be required by the protocol and is still, by definition, an adverse event.

#### **11.1.4 Serious Adverse Events**

A serious adverse event (SAE) is one that meets one or more of the following criteria:

- Results in death
- Is life-threatening (places the participant at immediate risk of death from the event as it occurred)
- Is disabling or incapacitating
- Results in inpatient hospitalization or prolongation of existing hospitalization
- Results in a persistent or significant disability or incapacity
- Results in a congenital anomaly or birth defect
- An important medical event that may not result in death, be life threatening, or require hospitalization may be considered an SAE when, based upon appropriate medical judgment, the event may jeopardize the participant or may require intervention to prevent one of the outcomes listed in this definition.

### **11.2 Safety Assessment and Follow-Up**

The PI will follow adverse events with start dates occurring any time after informed consent is obtained until 7 (for non-serious AEs) or 30 days (for SAEs) after the last day of study participation. At each study visit, the investigator (or designee) will inquire about the occurrence of AE/SAEs since the last visit. Events will be followed for outcome information until resolution or stabilization.

